- b. HIV medication adherence compared between study arms at 6 and 12 months (defined as  $>$ 90% adherence using 3-day pill recalls)
- c. Adverse events compared between study arms at 12 months (defined as Grade III-V adverse events including hypotension, peripheral edema, and other symptoms which may be related to amlodipine)
- d. Acceptability assessed through in-depth interviews with a subset of participants and providers

- e. CVD risk profile measured among all participants at enrollment including obesity, dyslipidemia, diabetes, smoking, physical inactivity, poor diet, and 10-year CVD risk (only among participants  $\geq$  40 years)
- f. Pre-existing myocardial and vascular dysfunction measured among all participants at enrollment using ECG, echocardiography and vascular ultrasound

**Study endpoints and analysis:** The primary endpoint is the difference in mean change in SBP (mm Hg) between study arms at 12 months. Secondary outcomes include viral suppression and medication adherence. We will also measure CVD risk factors among participants. We will compare the mean difference in change in SBP among participants using a linear mixed-effects model (LMM) accounting for repeated measures and correlations within subjects. We will assess incidence of HTN using Kaplan Meier methods. Dichotomized outcomes such as HTN will be analyzed via generalized linear mixed-effects model (GLMM) at all time points and via Fisher's exact test and logistic regression at 12 months. Viral suppression, medication adherence, and CVD risk factors will be compared between study arms using Fisher's exact test. Longitudinal data such as BMI and adherence will be analyzed using LMM and GLMM.

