HIV is associated with equal, if not greater, CVD risk as diabetes; yet, the WHO still recommends PLWH initiate antihypertensive treatment at the same BP threshold as adults without HIV. Data are needed to clarify if initiation of antihypertensive treatment among PLWH with pre-HTN can prevent progression to HTN, and ultimately CVD-related mortality. The proposed pilot trial is the first step to explore the feasibility, benefits, and risks of initiating antihypertensive treatment among PLWH with pre-HTN in a well-established HIV program in Haiti, one of the poorest countries in the world. Knowledge gaps include: Is it feasible to initiate and integrate antihypertensive treatment into HIV care among relatively healthy PLWH with pre-HTN? Could initiating antihypertensive treatment worsen HIV outcomes? What is the BP reduction using amlodipine (which is Haiti's first-line antihypertensive medication) among PLWH with pre-HTN? Data from this pilot trial will inform the design of a future multicenter trial powered for incident CVD events. **Our goal is to change guidelines** to lower the BP threshold for initiation of antihypertensive medications among PLWH, should earlier HTN treatment prevent CVD.

Table 2: Summary of WHO and Haitian HTN definitions and guidelines		
Category	Definition	Threshold for initiation of antihypertension treatment
Normal	SBP < 120 and DBP < 80	
Pre-HTN	SBP 120-139 or DBP 80-89	Diabetes & Chronic Kidney Disease (at SBP $\geq$ 130 or DBP $\geq$ 90)
HTN	SBP $>$ 140 or DBP $>$ 90	General adults including PLWH

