## 4 STUDY PROTOCOL

### 4.1 Study Objective

We propose a pilot randomized controlled trial to evaluate antihypertensive treatment among PLWH with pre-HTN at GHESKIO. This study will provide critical data on the feasibility, benefits and risks of antihypertensive treatment for CVD prevention among PLWH with pre-HTN that will inform a future definitive trial powered for incident CVD events. For the pilot study, we will enroll 250 PLWH (18-65 years of age) who have been on ART for  $\geq 1$  years with viral suppression within past 12 months and SBP 120-139 or DBP 80-89 mm Hg and no current antihypertensive treatment; randomize them to “early HTN treatment” or the current standard of care (SOC); and follow them for 12 months.

Amlodipine is the recommended first-line anti-hypertensive medication according to Haiti’s new primary care HTN guidelines. Participants in the early HTN treatment arm will initiate amlodipine 5 mg immediately, increasing to 10 mg if SBP  $>130$  mm Hg after 1 month. Participants in the SOC arm will initiate amlodipine only if they develop HTN (SBP  $\geq 140$  or DBP  $\geq 90$  mm Hg). We hypothesize that early HTN treatment will not impact viral suppression and be feasible and safe, with a reduction in BP at 12 months compared to SOC. The primary aim is to assess the feasibility of initiating antihypertensive treatment among PLWH with pre-HTN through a pilot randomized controlled trial comparing early HTN treatment to SOC. Feasibility outcomes include enrollment and retention data, proportion who initiate amlodipine, and incremental change in SBP at 12 months between arms. The secondary aim includes analyzing the following measures: viral suppression, HIV medication adherence, adverse events, acceptability, CVD risk profile, and pre-existing myocardial and vascular dysfunction.

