#### **4.4 Recruitment and Informed Consent**

Screening and recruitment will follow GHESKIO Clinical Trials Unit procedures that have been highly successful in NIH trials. We will identify and invite potential participants both 1) in-person at GHESKIO's HIV clinics using real time BP measurements and 2) from GHESKIO's electronic medical record (EMR) using BP measurements in the past 12 months, age, ART duration, viral suppression, and no current antihypertensive treatment. PLWH meeting these eligibility criteria will be tagged in the EMR as participants for recruitment and a list will be given to the study team.

The research nurse will approach patients in the HIV clinics, or call PLWH on the list to introduce the study and invite interested individuals for informed consent and then a screening visit. After confirming basic eligibility criteria, the research nurse will initiate informed consent procedures among eligible participants. The informed consent process consists of two education sessions, followed by assessment of understanding and written informed consent.

After informed consent, participants will be assigned a unique study ID number and undergo a screening visit with review of eligibility criteria and screening labs. Pre-HTN is defined as  $\geq 2$  BP measurements of SBP 120-139 mm Hg or DBP 80-89 mm Hg on separate days. All BP measurements will be done according to AHA/WHO guidelines. Screening labs will be collected (urine or serum pregnancy test, fasting or random glucose, and creatinine) to evaluate if the patient is pregnant, has diabetes, or kidney disease. We will document the number screened and reasons for study exclusion.

In 2018, 18,872 PLWH on ART received care at GHESKIO with mean duration of ART of 5.6 years, 76% on first-line regimens, 86% virally suppressed, and median age of 35 years. We estimate 3,819 PLWH at GHESKIO satisfy the eligibility criteria. Based on our past enrollment experience, we are confident 250 participants can be enrolled from this sampling frame in 6 months.

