#### 4.9 Analysis plan and statistical power considerations

**Sample size and power:** With a sample of 250 participants and 6 time points for BP measurements for each participant, we have 80% power with alpha 0.05 to detect a difference in change in SBP of 4 mm Hg or more between the study arms at 12 months (assuming consistent difference across time and a conservative correlation among measurement of 0.95). We will present summary statistics (e.g., mean and SD of pre, post, and difference within and between arms) in publication for readers and future meta-analyses.

**Aim 1:** Feasibility will be measured as the proportion of eligible participants willing to participate in the trial and their retention, and the proportion initiating amlodipine. We will compare the mean difference in change in SBP among participants from enrollment to 12 months in each study arm using linear mixed-effects model (LMM) accounting for repeated measures and correlations within subjects, where the time\*treatment interaction will serve as “primary” parameter addressing differential slopes for the two arms. We anticipate the two arms will have similar baseline characteristics due to randomization, and therefore the primary analysis will not adjust for baseline variables. If baseline variables are imbalanced, we will adjust factors in regression and report as sensitivity analysis. We will assess incidence of HTN using Kaplan Meier methods. We will analyze dichotomized outcomes (SBP <120 and DBP <80) at all time points via generalized mixed-effects model and at 12 months via Fisher exact tests and logistic regression. In other sensitivity analyses, we will explore the following issues: 1) compliance/adherence (e.g., per protocol analysis); 2) missing data/dropout (via last-value-carried-forward, multiple imputation or inverse-probability weighting); 3) competing risks (e.g., death); 4) joint modeling (of longitudinal and survival data); and 5) changepoint (of treatment initiation in SOC arm).

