**Aim 2:** The proportion of participants in each study arm with viral suppression (HIV-1 RNA < 1000 copies/mL) at 12 months will be compared between study arms using the Fisher exact test; we assume participants who are lost to follow-up or dead at 12 months will have HIV-1 RNA > 1000 copies/mL. Other categorical data including medication adherence, CVD risk factors (e.g. diabetes) will be analyzed similarly. Longitudinal data such as BMI and adherence (continuous or binary/categorical) will be analyzed accounting for repeated measures within participants, via LMM and GLMM as described above. We will also consider Generalized estimating equation-based method (so called, marginal or population-averaged model) and will report consistency or meaningful discrepancy. Acceptability will be assessed in qualitative interviews by [name] who is trained in qualitative research using interview information transcribed verbatim, translated into English, and then coded for analysis using a thematic coding scheme. We will also describe adverse events among all participants.

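### A hypothesis of no effect on viral suppression is paired only with a Fisher test of difference; no risk difference or interval is pre-specified

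*Combined protocol and SAP*

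**What the plan says.** Section 4.1 (Study Objective): "We hypothesize that early HTN treatment will not impact viral suppression and be feasible and safe". Section 2.2 (Scientific Rationale) lists among the knowledge gaps "Could initiating antihypertensive treatment worsen HIV outcomes", and says that the pilot will inform a later multicentre trial.

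For 12-month suppression (HIV-1 RNA below 1,000 copies/mL), section 4.9, Aim 2 says that the arm proportions "at 12 months will be compared between study arms using the Fisher exact test". Participants who are lost or have died count as unsuppressed. The Protocol Summary agrees: "Viral suppression, medication adherence, and CVD risk factors will be compared between study arms using" Fisher's exact test.

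Three other statements might seem to add something:

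- Protocol Summary: "Dichotomized outcomes such as HTN will be analyzed via generalized linear mixed-effects model (GLMM) at all time points", with Fisher's test and logistic regression at 12 months.
- Section 4.9, sample-size paragraph: "We will present summary statistics (e.g., mean and SD of pre, post, and difference within and between arms").
- Section 4.9, Aim 2: mixed models, and possibly GEE, for longitudinal data, with BMI and adherence as the examples.

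The only power statement in the plan concerns systolic blood pressure.

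**The concern.** Fisher's test asks whether the data contradict equal rates. Failing to reject may mean that there is no effect, or that the sample is too small to show one. The question in section 2.2 is about harm, so the useful result is how large a loss of suppression the data exclude. A p-value does not give that.

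The plan does not say that p > 0.05 will be read as no impact, and it does compare arm proportions. The gap is that the quantity needed to judge the hypothesis is not pre-specified. A non-significant result could then be carried into the design of the larger trial as reassurance that the data do not provide.

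A lesser matter is that no analysis restricted to measured viral loads is named beside the rule that counts missing as unsuppressed.

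**Working it through.** **Does other text supply an interval?**

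- The summary statistics in section 4.9 are illustrated by means and SDs, in the paragraph on blood-pressure power. No interval for a difference in proportions is named.
- The dichotomised-outcomes sentence in the Protocol Summary could be stretched to cover suppression, but the sentence after it assigns suppression to Fisher's test alone. In section 4.9, logistic regression at 12 months is tied to a blood-pressure dichotomy.
- The mixed-model and GEE text is for longitudinal data. After enrolment, viral load is scheduled once, at month 12 (section 4.6, Table 4).

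**Inputs**

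- 250 participants (4.9) randomised 1:1 (4.5): 250 / 2 = 125 per arm.
- Alpha is 0.05 for blood pressure (4.9). None is stated for Fisher's test, so two-sided 0.05 is assumed.
- Suppression rate: the only figure is clinic-wide for 2018 (4.4): "76% on first-line regimens, 86% virally suppressed, and median age of 35 years". Entrants are on ART "with viral suppression within past 12 months", so the trial rate may be higher. SOC rates of 86%, 90%, 95% and 98% are assumed.
- The plan states no power or precision for suppression, so there is no figure of its own to reproduce.

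**Method.** Every pair of counts from two independent binomials (n = 125 each) is enumerated and weighted by its probability. Fisher two-sided p < 0.05 counts as significant. The interval for d = p(early) − p(SOC) is Newcombe's, built from the Wilson limits (l, u) of each arm:

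- lower = d − √[(p_E − l_E)² + (u_S − p_S)²]
- upper = d + √[(u_E − p_E)² + (p_S − l_S)²]

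**Results by assumed SOC rate**

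| | 86% | 90% | 95% | 98% |
|---|---|---|---|---|
| Fisher misses a true 5-point loss | 0.857 | 0.831 | 0.765 | 0.647 |
| Fisher misses a true 10-point loss | 0.539 | 0.462 | 0.302 | 0.144 |
| p ≥ 0.05 and lower limit ≤ −10 points, equal true rates | 0.369 | 0.258 | 0.074 | 0.003 |
| Same event, true 5-point loss | 0.672 | 0.615 | 0.473 | 0.261 |
| Mean interval half-width, equal true rates (points) | 8.7 | 7.7 | 5.9 | 4.4 |

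The 10-point line is for illustration only and is not a proposed margin.

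**Single tables**

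- 107/125 in each arm: the Wilson limits are 0.784 and 0.907 around 0.856. The half-width is √(0.072² + 0.051²) = 0.088, so the interval is ±8.8 points.
- 122/125 in each arm: ±4.7 points.
- Early 95/125 v SOC 108/125: p = 0.051, difference −10.4 points, 95% CI −20.0 to −0.7.
- Early 114/125 v SOC 122/125: p = 0.051, difference −6.4 points, 95% CI −12.9 to −0.6.

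The first two tables both give p = 1, yet they exclude very different losses. The last two are both non-significant, yet neither supports a claim of no impact.

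**Missing counted as unsuppressed.** At 98% retention in both arms (4.6), 90% v 80% becomes 0.98 × 90 − 0.98 × 80 = 9.8 points instead of 10. If retention differed, say 95% v 98% (hypothetical) with 95% truly suppressed in both arms, the apparent loss would be 0.95 × (98 − 95) = 2.85 points.

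**The case against.** The strongest reply is that this is an unpowered secondary outcome of a pilot whose primary aim is feasibility. Fisher's test is valid for the table. The plan makes no equivalence or non-inferiority claim, and the hypothesis is one clause of a sentence that also covers feasibility, safety and blood pressure. If arm proportions are published, any reader can compute the interval. The eligibility rules (at least a year on ART, a stable regimen, recent suppression, no ritonavir-boosted protease inhibitor, not judged unstable on ART) point to suppression above 86%. At 95–98% the chance of an inconclusive result with equal true rates is only 7.4% to 0.3%. Placing an interval beside the p-value would be enough.

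Much of this stands. The test is not invalid, no misreading is planned, the size depends on an unknown rate, and the miss rates describe low power that an interval does not cure. The missing-data point is minor. What does not stand is that the gap is harmless. A reader's later calculation is not a pre-specified analysis, and a pilot's task is to estimate. At 98% suppression Fisher's test still misses a true 5-point loss in 65% of trials. Adding an interval without ranking it is also incomplete, because it can disagree with Fisher's p-value and the plan should say beforehand which one counts.

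**Conclusion.** The concern holds. The one analysis named for viral suppression cannot support the hypothesis stated for it, and no other text supplies a risk difference or interval. The mismatch in logic exists at any suppression rate; its practical size depends on a rate that the documents do not give. The figures rest on 125 per arm, two-sided 0.05, independent binomials and the four assumed SOC rates. This should be changed, but it does not threaten the primary outcome, and a powered non-inferiority test is not required.

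**What to change.** - **Section 4.9, Aim 2, and the matching Protocol Summary text:** make the main result the risk difference (early minus SOC) in 12-month suppression with a two-sided 95% confidence interval, by Newcombe or Miettinen-Nurminen. Keep Fisher's p-value as supplementary and state that the interval governs interpretation.
- **Section 4.1:** reword the hypothesis as estimating the effect of early treatment on suppression. A margin is optional and would be for the sponsor to justify.
- **Secondary addition:** report missing viral loads by arm, and add a sensitivity analysis on measured viral loads only.

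The cost is wording; no extra data, visits or participants are needed. There are two downsides. The result may have to be reported as inconclusive, which is more likely at 86–90% suppression than at 95% or above. The interval and Fisher's p-value can also disagree at the edge: early 116/125 v SOC 123/125 gives p = 0.060 with a CI of −11.6 to −0.3 points. By enumeration, the Newcombe interval excludes zero while p ≥ 0.05 in 1.5–1.8% of trials with equal true rates and in 4–10% with a true 5-point loss. Its coverage stays between 0.951 and 0.977 across the scenarios examined, so letting it govern is defensible.

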#### 4.10 Timeline

This study will be conducted over two years (8 quarters). In Q1, we will finalize study operating procedures, data collection tools, and staff training. Screening, recruitment, and enrollment will be conducted in Q2-3. Participants will be followed for 12 months from Q2 to Q7. In-depth interviews will be conducted at 12-month clinic visits during Q6-7. In Q7-8, we will finalize data analysis and dissemination.

#### **4.11 Potential challenges and solutions**

Insufficient number of eligible individuals to meet target: We will monitor enrollment weekly and expand recruitment to other GHESKIO-affiliated clinics if needed. Missing data and migration: GHESKIO's CTU has a history of >98% retention in clinical trials. We will conduct the 12-month questionnaire by phone among those who cannot return. Since the treatment initiation threshold varies across study arms, blinding is not feasible. We will explore the use of placebo and blinding for the future trial.

#### **4.12 Summary and future directions**

There is an urgent need for CVD prevention among PLWH with elevated BP who have alarmingly high risk of CVD events and related mortality. This study is the first step towards evaluating the safety and benefits of earlier HTN treatment among PLWH and will inform a larger trial powered for CVD events. If we demonstrate feasibility and find benefit, the larger trial to follow may shift the paradigm of antihypertensive treatment for CVD prevention in PLWH, both in the US and abroad.

#### **4.13 Data Safety and Monitoring Board and Procedures:**

The following monitoring steps will be taken to monitor and ensure the safety of research volunteers:

- The study and consent forms must be approved by Institutional Review Boards in Haiti and Weill Cornell prior to the start of the trial.
- The Principle Investigator will receive a weekly log of adverse events and will review this log each week with the local study team and international collaborators.
- The study team is responsible for reporting all severe Grade III-V adverse events or death suffered by study participants to the IRBs and DSMB within 24 hours of knowing of the event.
- The Principle Investigator must renew IRB approval every year through submission of an annual update including a description of all adverse events.

A Data Safety Monitoring Board (DSMB) will ensure the safety of trial participants through monitoring study procedures, implementation, study findings and review of all adverse events including social harms

The DSMB will meet before enrollment starts to review the study protocol for protection of human participants. The DSMB will then meet every six months. Prior to their meeting, they will receive summary reports of study progress, all adverse events including loss of confidentiality, stigma, social harms and Grade III-V adverse events reported by a study participant. Any severe adverse event, Grade III or IV or death will be reported to the DSMB Chair, within 24 hours of documentation by study staff, who will also report it to [name] (PI) and [name] (Haitian Site PI). After each meeting, the DSMB will provide a written report on the status of the study and their recommendations for any modifications of the study. This report will be provided to the PI and IRBs. The DSMB had the right to halt the study for safety concerns at any time.

